### **5.7 Evidence-Based Program**

MINDxYOU is a self-guided online intervention based on third-wave psychotherapies, including mindfulness, compassion, acceptance, and spirituality. It consists of four modules

and includes videos, readings, guided audio exercises, and downloadable resources to integrate practices into daily healthy habits (e.g., physical activity, sleep, diet, socialization).

The program starts with a welcome module where participants share their stress factors and receive motivational feedback to encourage adherence. Each module includes explanatory videos, key content, and practical exercises. Participants are encouraged to complete each module over two weeks. Module 1 focuses on applying mindfulness and compassion to healthy lifestyle areas. The program lasts approximately 8 weeks.

A recent study showed significant reductions in perceived stress among participants who completed at least three of the four modules. Improvements were also noted in depression, anxiety, somatization, resilience, self-compassion, and some mindfulness facets (López-Del-Hoyo et al., 2025).

## 6. Data Analysis

For the implementation analysis, outcomes will be assessed following the framework by Hermes et al. (2019) and Proctor et al. (2011). Passive data will include objective usage metrics (e.g., logins, frequency of use, completed modules, tasks submitted). Quantitative data from questionnaires will be analyzed using appropriate statistical methods, while qualitative data will be gathered through stakeholder interviews.

For the clinical analysis, variables will be described using mean and 95% confidence intervals for normally distributed quantitative variables, or medians and interquartile range for non-normally distributed data. Effectiveness variables (stress, anxiety, and depression) will be compared using paired-samples t-tests.

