### **3. Hypotheses**

1. Primary hypothesis (implementation): Implementing the MINDxYOU program in healthcare settings will be feasible, acceptable, and sustainable among healthcare professionals.
2. Secondary hypothesis (clinical effectiveness): Participants using the program will experience a significant reduction in perceived stress, anxiety, and depressive symptoms compared to baseline.
3. Adherence hypothesis: Program usage and participant satisfaction will be positively associated with perceived ease of use and perceived effectiveness of the intervention.
4. Barriers and facilitators hypothesis: Factors such as work overload and lack of time may hinder program adoption, while accessibility and the flexibility of the online format will facilitate its integration into the routines of healthcare professionals.

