### **4. Objectives**

Primary Objective:

To evaluate the feasibility, acceptability, and sustainability of implementing the MINDxYOU program in real-world healthcare settings.

Secondary Objective:

To assess clinical outcomes of the intervention, including its effects on perceived stress, anxiety levels, and depression symptoms among healthcare professionals.

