### **5.5 Sample Size**

For the pilot study, a sensitivity analysis was conducted using a paired samples t-test, assuming a moderate effect size (Cohen's  $dz = 0.46$ ), 95% confidence level ( $\alpha = 0.05$ ), and 80% statistical power. The required sample size was determined to be  $N = 30$ . For the full study, the same analysis was applied with a smaller effect size (Cohen's  $dz = 0.25$ ), resulting in a required sample size of  $N = 100$ .

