### **5.6 Procedure**

Recruitment strategies will include posters and brochures in hospitals and primary care centers, as well as presentations in group sessions with healthcare professionals, including those attending occupational stress consultations. Email invitations will include a brief explanation of the study and a web link to the platform. Participants will be required to submit signed informed consent electronically. Eligibility will be verified, and those meeting inclusion criteria will be formally enrolled. Participants will receive a welcome email with platform login credentials. Instructions on how to use the platform will be provided in the welcome module.

Participants will be assessed on all study variables every 8 weeks. Usability (SUS) will be assessed after completing Modules 1 and 4. Platform usage will be tracked (logins, completed modules, submitted tasks).

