## 7. Ethics and Dissemination

All procedures will follow the Declaration of Helsinki (1964 and subsequent amendments; latest version adopted at the 64th WMA General Assembly, Fortaleza, Brazil). Signed informed consent will be obtained from all participants, who will not receive any financial compensation. Participants will be informed about study procedures, potential risks, and their right to withdraw at any time.

Major protocol modifications (e.g., changes in eligibility, outcomes, analysis) must be approved by ethics committees. Data confidentiality will comply with Spanish Organic Law 3/2018 on Data Protection and Digital Rights, aligned with the EU GDPR. A specific plan will be implemented to ensure maximum data security, using two separate systems and databases: one for personal data and one for clinical data, hosted on separate servers.

Study results will be published in peer-reviewed biomedical journals and presented at national and international conferences. Reporting will adhere to the StaRI (Standards for Reporting Implementation Studies) statement (Pinnock et al., 2017).

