## 10. Study Limitations and Strengths

This study's strengths include its innovative implementation focus, accessible online format, evidence-based design, and applicability across various healthcare environments. However, limitations include possible low adherence, lack of a control group, variability in participation, and dependence on technology. Its potential integration into the public health system makes it a valuable resource for supporting healthcare workers' mental health, reducing demand on mental health services, and improving patient care quality.

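### Paired t-tests as the only clinical comparison leave the secondary outcomes open to bias if questionnaire loss relates to baseline score; a mixed model reported beside them, with a shift analysis, is a cheap improvement

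*Protocol*

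**What the plan says.** - Protocol, section 6 (Data Analysis): "Effectiveness variables (stress, anxiety, and depression) will be compared using paired-samples t-tests". This is the only comparison given for the clinical outcomes.
- Section 5.5 (Sample Size) uses the same test: "a sensitivity analysis was conducted using a paired samples t-test", with dz 0.46 for the pilot (N = 30) and dz 0.25 for the full study (N = 100).
- Section 5.6 (Procedure): "Participants will be assessed on all study variables every 8 weeks". The number of assessments is not given. Section 5.7 adds: "The program lasts approximately 8 weeks". Week 8 is therefore both the first follow-up and the end of the programme.
- Section 10 (Limitations): "limitations include possible low adherence, lack of a control group, variability in participation". No questionnaire return rate appears anywhere.
- Section 3 (Hypotheses) makes the clinical hypothesis secondary and within-group: "Participants using the program will experience a significant reduction in perceived stress, anxiety, and depressive symptoms compared to baseline".

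**The concern.** A paired t-test on observed data drops everyone who lacks one of the two scores, and it ignores any further 8-weekly scores. The programme is self-guided and online, its users are busy staff, and the protocol itself expects uneven participation. Incomplete follow-up is therefore plausible, although using the modules and returning questionnaires are different things.

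Suppose the people who return questionnaires started with higher or lower stress than those who do not. The mean change among completers then differs from the mean change among all enrolled, even when nothing has changed on average. The named test could show a reduction that did not occur or hide one that did. The baseline scores that would correct this part are already collected.

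**Working it through.** **1. The plan's own figures.** n = ((z_alpha + z_beta)/dz)². One-sided 5%, 80% power: (2.487/0.46)² = 29.2, so 30; (2.487/0.25)² = 99.0, so 99. The exact noncentral t gives 31 and 101. The stated 30 and 100 are thus reproduced by a one-sided test. Two-sided, 40 and 128 are needed. Sidedness is a separate matter; here dz 0.25 serves only as a yardstick.

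**2. Formula.** Take improvement as baseline minus follow-up, in baseline SDs, with equal SDs and correlation r, so that the slope of follow-up on baseline is r. Let D be the mean baseline of those with both scores minus the mean baseline of all enrolled. If return depends on baseline only,

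bias of the paired change = (1 − r) × D, or in dz units (1 − r) × D / √(2(1 − r)).

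**3. Inputs.**
- r = 0.77 is the stress scale's test-retest value in section 5.4. It is not this study's baseline-to-follow-up correlation and does not cover the other scales, so r = 0.5 is shown as well. The scaling √(2(1 − r)) is 0.678 and 1.0.
- Return of 50%, 80% and 90% is assumed, as is an odds ratio of return of 2 or 0.5 per baseline SD. At 50% return, an odds ratio of 2 means 67% return at +1 SD and 33% at −1 SD, which is strong dependence.
- D follows from the logistic return model: about ±0.312, ±0.13 and ±0.066.

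**4. Results, return related to baseline.** At r = 0.77 and 50% return: 0.23 × 0.312/0.678 = 0.106. At r = 0.5: 0.5 × 0.312/1.0 = 0.156. In the last two columns the first figure is for odds ratio 2 and the second for 0.5.

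| Return | Bias, r = 0.77 (dz) | Bias, r = 0.5 (dz) | Paired estimate if true dz is 0.25 (r = 0.77) | Favourable false positives, no true change (N = 100, r = 0.77; nominal 2.5%) |
|---|---|---|---|---|
| 50% | ±0.11 | ±0.16 | 0.36 or 0.14 | 11% or 0.4% |
| 80% | ±0.04 | ±0.06 | 0.29 or 0.21 | 6% or 0.8% |
| 90% | ±0.02 | ±0.03 | 0.27 or 0.23 | 4% or 1.5% |

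The false-positive rates come from 20,000 simulated trials per setting, and the simulated biases agree with the formula. The two-wave likelihood estimate (completers' regression evaluated at the mean of all baselines) had bias 0.00 and favourable false positives of 2.2% to 2.6% throughout. In the pilot (N = 30, 50% return, odds ratio 2) the bias is the same, with false positives of 5.7% against 2.3%.

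Milder dependence matters less. At 80% return and r = 0.77, an odds ratio of 1.5 gives 0.026 dz and 4.2%; an odds ratio of 1.25 gives 0.014 dz and 3.3%.

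**5. Random loss.** Neither method is biased. Two-sided power at dz 0.25 is 41% (paired) against 42% (likelihood) at 50% return, and 60% against 61% at 80%. With no loss it is 70%.

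**6. Where the model does not help (r = 0.77).**
- Return related to the improvement itself (odds ratio 1.5 per SD): paired bias 0.20, model 0.18 dz at 50% return; 0.08 and 0.07 at 80%. About a tenth is removed, or about a quarter at r = 0.5.
- Return related to the unseen follow-up score (odds ratio 0.5 per SD): paired 0.11, model 0.20 dz at 50% (false positives 11% and 28%); 0.04 and 0.08 at 80%. The model is about twice as biased, or about 1.5 times at r = 0.5.

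**7. Range for the shift analysis.** The shift in missing scores that cancels the model's bias is bias × SD of change/(1 − return). For loss tied to the follow-up score at r = 0.77: 0.199 × 0.678/0.5 = 0.27 and 0.080 × 0.678/0.2 = 0.27 baseline SD. For loss tied to the change it is 0.24. At r = 0.5, follow-up-related loss needs about 1.5 × 0.156 × 1.0/0.5 = 0.47. A grid to 0.5 SD just covers these settings.

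**The case against.** - **The protocol names a test and does not prescribe complete cases.** A reader might infer that it fixes a complete-case analysis. It does not: a paired t-test can be run on imputed data, and imputation may be specified in an analysis plan that is not shown. This stands. The point therefore rests on the stated choice of test and holds only absent imputation. Imputation based on the baseline score would meet most of it.
- **Nothing is shown to be wrong.** The test fits a single-group, change-from-baseline hypothesis. Low adherence is not the same as lost questionnaires, and no passage says that loss follows stress. This stands too: a reader might infer that the clinical results will be biased, and the documents support only that they could be.
- **The model is not better under every mechanism.** True, as step 6 shows, and no passage says which mechanism is likelier. Replacing the t-test by the model alone would not be justified.
- **The target is arguable.** Section 3 speaks of participants who use the programme, while section 4 speaks of healthcare professionals. Reporting both analyses serves both readings.
- **The check is simple.** It used two waves and normal data. Skewed scores and more than two waves were not simulated.

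**Conclusion.** The point holds as a conditional, optional improvement to the secondary clinical results. If loss relates to baseline score with an odds ratio of 2 or 0.5 per SD, the paired change is off by about 0.11 to 0.16 dz at 50% return, 0.04 to 0.06 at 80% and 0.02 to 0.03 at 90%. Against dz 0.25, that is 44% to 64%, 16% to 24% and 8% to 12%. The return rates, odds ratios and the lower correlation are assumptions. With complete or random follow-up the bias is zero.

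Two stronger readings go too far. One is that the study's main conclusions are at risk: those concern feasibility, acceptability and sustainability, which these tests do not address. The other is that moving to a mixed model leaves the planned sample size adequate: the model does not restore power lost to dropout. Nor does either method make up for the missing control group, which section 10 already concedes.

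**What to change.** In section 6, for each clinical outcome:

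1. Analyse all enrolled participants who have a baseline score, including those with nothing later, by a likelihood-based linear mixed model. Use all collected scores, categorical time and correlated within-person errors, with baseline to week 8 as the main contrast.
2. Report the paired t-test beside it, labelled as the result in those with both scores.
3. Add a shift (delta) sensitivity analysis: impute missing week-8 scores from observed scores, shift them by, for example, 0, ±0.25 and ±0.5 baseline SD, and report the shift at which the conclusion changes.

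**Cost.** No new data, about three sentences of text and a little more analysis work. Ethics approval may be needed, since section 7 says: "Major protocol modifications (e.g., changes in eligibility, outcomes, analysis) must be approved by ethics committees". With two complete waves the model and the t-test give the same estimate. The real downside is the one in step 6 of the working: the model removes little of the bias if loss depends on the change itself, and does worse than complete pairs if loss depends on the unseen follow-up score. That is why the t-test stays and the shift analysis is added.

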## 7. Ethics and Dissemination

All procedures will follow the Declaration of Helsinki (1964 and subsequent amendments; latest version adopted at the 64th WMA General Assembly, Fortaleza, Brazil). Signed informed consent will be obtained from all participants, who will not receive any financial compensation. Participants will be informed about study procedures, potential risks, and their right to withdraw at any time.

Major protocol modifications (e.g., changes in eligibility, outcomes, analysis) must be approved by ethics committees. Data confidentiality will comply with Spanish Organic Law 3/2018 on Data Protection and Digital Rights, aligned with the EU GDPR. A specific plan will be implemented to ensure maximum data security, using two separate systems and databases: one for personal data and one for clinical data, hosted on separate servers.

Study results will be published in peer-reviewed biomedical journals and presented at national and international conferences. Reporting will adhere to the StaRI (Standards for Reporting Implementation Studies) statement (Pinnock et al., 2017).

## 8. Study Timeline

ACTIVITY 1: Implementation Study (2025–2026) 1.1 Pilot study at Regional University Hospital of Málaga1.2 Implementation within the Andalusian Health Service (SAS): - Intervention delivery, coordination meetings with healthcare staff- Participant recruitment and online treatment administration- Post-treatment protocol evaluation, platform maintenance, technical support- Collection of acceptability and appropriateness data, focus groups with professionals and managers

ACTIVITY 2: Data Analysis and Interpretation (2026–2027) - Research team meetings; quantitative and qualitative data analysis- Final report preparation

ACTIVITY 3: Dissemination and Exploitation of Results (2027) - Preparation of manuscripts; dissemination through professional events, health agencies, social media, and media outreach

## 9. Funding and Resources

This project is supported by a 3-year Junior Postdoctoral contract funded by the Andalusian Government (CSyC 2024 – Postdoctoral Grants, Ref: RHJ-0043-2024). The study is based at the Research Unit of the Mental Health Clinical Management Unit at the Regional University Hospital of Málaga, part of the Biomedical Research Institute of Málaga (IBIMA), which provides the infrastructure required for conducting the research. Resources from the Mental Health UGC will cover costs such as software licenses.

Personnel: Junior Postdoctoral Researcher (36 months) – €125,514  
Technical: Moodle license – €2,000 annually

## 10. Study Limitations and Strengths

This study's strengths include its innovative implementation focus, accessible online format, evidence-based design, and applicability across various healthcare environments. However, limitations include possible low adherence, lack of a control group, variability in participation, and dependence on technology. Its potential integration into the public health system makes it a valuable resource for supporting healthcare workers' mental health, reducing demand on mental health services, and improving patient care quality.

## 11. Discussion

This implementation study of the MINDxYOU program provides key insights into the feasibility, acceptability, and sustainability of a digital mental health intervention for healthcare professionals. Findings will evaluate how mindfulness-, compassion-, and acceptance-based strategies can be effectively integrated into real clinical settings (Bauer & Kirchner, 2020).

A key strength of this study lies in its implementation science approach, addressing both barriers and facilitators of adoption in the Andalusian Health Service. Identifying these factors is essential for designing strategies that support the sustainable and scalable use of

MINDxYOU. The Hybrid Type III design advances implementation science by simultaneously assessing clinical effectiveness and contextual influences (Proctor et al., 2011).

Preliminary evidence suggests MINDxYOU can significantly reduce perceived stress and improve healthcare professionals' psychological well-being (López-Del-Hoyo et al., 2025). However, real-world implementation may face challenges, including adherence and acceptance by participants. Results will be essential to evaluate the program's feasibility in busy clinical workflows.

Digital platforms for mental health gained rapid acceptance during the COVID-19 pandemic, representing a paradigm shift in healthcare delivery. Still, questions remain about their long-term quality, accessibility, and effectiveness. This study includes usability and acceptability metrics to empirically evaluate healthcare professionals' engagement and identify factors that could enhance implementation (Bangor et al., 2008).

From a clinical perspective, results may help bridge the gap between research and care, supporting routine use of evidence-based interventions. Findings can inform program adaptations and scalability for other high-stress populations. Ultimately, improving healthcare workers' mental health may also enhance patient care quality. Effective implementation strategies could guide future digital health interventions, benefiting both the workforce and the healthcare system as a whole.
